Appendix C (The IRB-approved Protocol)

Primary objectives:

- 1) Identify and characterize factors affecting children's exposures to chemical ingredients from consumer products found in their everyday environment in order to support the data and modeling needs of the exposure components of EPA's national research programs;
- 2) Evaluate the pilot study data metrics for incorporation in and enhancement of CDC's ability to understand the relationship between environmental exposures and asthma in green versus traditional low-income housing;
- 3) Compare multimedia measurements and survey data between pre- and post-renovation time points in green and traditional low-income housing to assess exposure related changes in the residence and participants due to renovation activities.

Objective 1 will examine how influential personal, housing, and community factors are in determining children's exposures. Results will be used to directly compare siblings and determine how personal and housing factors vary. For siblings living in the same household, we hypothesize that shared exposures to housing and community factors both before and after building renovation will be similar. Thus, we hypothesize that personal exposure factors, including activities and behaviors, will most influence exposure to chemical and biological agents found in their indoor environment. Furthermore, the variability in personal exposure factors will be a function of age, lifestage, and health status (asthma versus no asthma). We can use this information to parameterize, refine, and evaluate exposure and dose models for consumer product active ingredients. Because of the lack of data on personal, housing, and community factors from the same cohort, it is necessary to collect these data to evaluate this objective.

Objective 2 will evaluate the pilot study methods and approaches for measuring exposures to consumer product chemicals and identifying exposure factors. It will also establish suitability for incorporation in future Green Housing Study sites and for future research directions. Our data collection effort is intended to complement the multimedia measurements and information being collected by CDC in the Green Housing Study. Methods found to be suitable in the pilot study will allow EPA and CDC to improve the evaluation of relationships between environmental exposures and asthma in the renovated and non-renovated homes.

Objective 3 will examine how exposure changes throughout the renovation period and differences between renovated and non-renovated homes. All multimedia measurements, activity pattern information, and survey data will be used to evaluate changes in exposure over time. Results will be used to directly compare various time points for exposure. We hypothesize that the types of chemicals the children are exposed to during the post-renovation period are significantly different than the chemicals the children are exposed to prior to renovation, and that differences between renovated and non-renovated homes will be observed.

Appendix C (The IRB-approved Protocol)

Secondary objectives:

- 4) Evaluate exposure to chemicals in household cleaning and personal care products as a modifying factor in interpreting the effectiveness of green housing renovations on reducing the incidence of asthma-like symptoms;
- 5) Examine the relationships between consumer products in a residence, environmental concentrations, and exposure to active ingredients found in consumer product chemicals to support development and evaluation of models for predicting exposure to these chemicals;
- 6) Measure biomarkers of consumer product chemicals for young children in conjunction with environmental measurements to evaluate exposure and dose models;
- 7) Assess rapid, low burden, low cost methods for characterizing consumer product use in the residential environment to predict exposure to chemicals;
- 8) Use low burden techniques and survey instruments to collect current information on children's activities, locations, and dietary habits to support exposure models and databases;
- 9) Use settled dust to identify and classify indoor fungal populations and functions overrepresented among fungal biota;
- 10) Evaluate the feasibility of using a simplified mass balance approach to estimate chemical exposure and dose rates incorporating children's toenail clippings, other multimedia measurements, and activity information;
- 11) Examine the feasibility of obtaining extant community-level data and prepare draft approaches for using such data for children's community exposure factor assessment and multiple stressor effects on estimates of health risks.

To accomplish objective 4 we will collect information on the types of household cleaning and personal care products used inside the home as well as information on the duration and frequency of their use. We will examine the association between the primary risk factor (renovation status) and the outcome (symptom incidence) to evaluate possible modifying effects due to chemicals emitted from consumer products, controlling for medication use. We hypothesize that exposure to household cleaning and personal care products will change the relationship between incidence of asthma-like symptoms and renovations to green housing standards.

Objective 5 will support development and evaluation of models for predicting exposure to consumer product chemicals. Measurement and survey results will be analyzed for linkages to the potential for exposure.

To evaluate exposure and dose models, chemical concentrations (parent and metabolite(s)) need to be measured in both environmental and biological matrices in order to serve as data inputs. Select pesticides and their metabolites have been used to evaluate various exposure models (e.g.,

Appendix C (The IRB-approved Protocol)

SHEDS-Multimedia); however, few model evaluations have been conducted for other chemical types. These models need to be evaluated for consumer product active ingredients because of their prevalence in the indoor environment and potential asthma morbidity in young children from potential exposures. Biomarker measurements will be collected in order to evaluate objective 6. Results from objective 2 will be employed to assist in these analyses.

To accomplish objective 7 we will evaluate a novel method for rapidly characterizing consumer product inventories in the residential environment. We hypothesize that pictures can be used to adequately capture information on consumer products being used in the home. The results from this effort will then be used to predict exposures to chemicals.

There is a lack of current information on children's activities, locations, and dietary habits, and objective 8 will generate such information. We hypothesize that children's activities, locations, and dietary habits are dependent on age, lifestage, and factors related to their home and community. In combination with multimedia measurements being collected in the Green Housing Study, results from this objective will be used to estimate aggregate and cumulative exposures.

Results from objective 9 will be used for the DNA analysis of mold from dust and measurements of the ERMI values at each time point. We hypothesize that the electrostatic dust collection method is adequate to collect enough dust for DNA analysis. From these electrostatically collected molds, DNA will be extracted and analyzed using HTS analysis. HTS technologies provide the opportunity to holistically explore and identify diverse indoor fungal populations. In addition, the metagenomic data generated from the DNA of dust samples will be used to identify genes and functions that are overrepresented among the fungal biota.

The data collected for objective 10 will be used to explore the feasibility of using a simplified mass balance approach to estimate chemical exposure and dose rates for very young children. The goal of this objective is to evaluate the relationship between toenail clippings, blood, feces, duplicate diet, and dust to determine the feasibility of using these multimedia measurements to estimate chemical exposure and dose rates for very young children in observational exposure measurement studies. Associations between potential sources, exposure pathways, and indoor/outdoor concentrations will be evaluated. We hypothesize that toenail clippings can be used as a surrogate for blood concentrations and linked with various environmental measurements to develop a new approach to estimate chemical exposure and dose rates. If proven feasible, this approach could be applied to future epidemiological studies to generate current data on chemical exposure and dose rates.

Analysis of data for objective 11 will be used to understand the feasibility of collecting extant data on community exposure factors and how these factors may be applicable to other types of exposures and outcomes.

Appendix C (The IRB-approved Protocol)

2.3 Sample Size Considerations

The sample size for the EPA pilot study add-on is fixed and dependent on CDC's grantee's ability to recruit and retain participants. Using available chemical concentration data for limonene (Sarigiannis et al., 2011), we can estimate the effect sizes we can see given various sample sizes (assumptions: design effect = 2.0, statistical power = 0.8, alpha level = 0.05, correlation = 0.3).

Example: Limonene in air ($\mu\text{g}/\text{m}^3$)

If non-renovated homes have a mean concentration and standard deviation = $15.0 \pm 19.4 \mu\text{g}/\text{m}^3$, with a fixed sample size of $n=35$ participants in each group (renovated and non-renovated homes), we could see a minimum size difference of $11.9 \mu\text{g}/\text{m}^3$.

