3.2 Study Location

The third study site will be determined by CDC based on site selection criteria detailed in their funding opportunity announcement. In the Green Housing Study third study site, the target sample size is 32 green renovated homes and 32 comparison homes. The target sample size for the EPA pilot study add-on is the same number of families as are recruited to participate in the Green Housing Study. Thus, n=64 younger siblings (only one sibling per household) will be the maximum number that could be enrolled as part of the EPA pilot study add-on. Participants in each family will include the index child and a sibling of the index child living in the same household, as well as the mother/caregiver. The index child is defined as the child recruited to participate in the Green Housing Study who ranges in age from 7-12 years with a doctor diagnosis of asthma. By including both the index child and a sibling, it is an opportunity to collect exposure information for two children living in the same household, allowing us to explore differences in exposure based on lifestage.

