Appendix C (The IRB-approved Protocol)

measurements and health outcomes between the arms, we began by calculating sample sizes based on each of these measures.

Our sample calculations for environmental measurements (see Table 21) were based on cockroach allergen data in a repeated measures study of the effect of an integrated pest management (IPM) intervention, which indicate that 13 buildings would be necessary in each of the two arms of the study, assuming that 25 subjects could be recruited for each building, yielding 325 subjects/study arm to provide adequate statistical power for environmental measurements.

Our sample calculations for health outcomes (see Table 22) were based on asthma in children subjected to a multifactorial intervention (i.e., education, mattress covers, IPM, and HEPA filter units) in a repeated measures study. These data indicate that 274 subjects/study arm would be needed to provide adequate statistical power for asthma outcomes.

Therefore, since we desired sufficient power to detect meaningful differences in both 1) environmental measurements and 2) health outcomes, we selected the larger of the two estimates — 325 subjects/study arm — as the minimum sample size (see Figure 7). In addition, we augmented this number in order to account for an anticipated 20 percent loss to follow-up over a one-year period. After rounding up where necessary, this increased the sample size to 416 subjects/study arm, comprising 32 subjects (one subject per apartment) in each of 13 buildings in each study arm. The total sample size for the study across both study arms is 832 subjects. The details of our sample size calculations are listed below and the equations that were used were from a book on longitudinal data analysis by Diggle, Liang, and Zeger (1994).

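### Section 2.3's detectable difference of 11.9 µg/m³ uses 35 per group where the site targets 32 homes, and rests on an unstated one-sided test with no allowance for loss

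*Protocol*

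**What the plan says.** Protocol Section 2.3 lists its inputs as "assumptions: design effect = 2.0, statistical power = 0.8, alpha level = 0.05, correlation = 0.3". It takes limonene in air as the example: "If non-renovated homes have a mean concentration and standard deviation = $15.0 \pm 19.4" µg/m³. The result is for 35 per group: "with a fixed sample size of $n=35$ participants in each group (renovated and non-renovated homes), we could see a minimum size difference of" 11.9 µg/m³. The section does not say whether the test is one- or two-sided, or how many repeated measures the correlation applies to. It says the sample depends on recruitment and retention, but applies no loss.

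Elsewhere the protocol gives a different number of homes. Section 2.1 includes 32 green and 32 comparison homes, and Section 3.2 says "the target sample size is 32 green renovated homes and 32 comparison homes". Sections 2.4 and 3.2 cap siblings at 64, one per household. Section 4.4.1 takes the indoor air sample from the main play area of the home. Appendix A (Part B, B.1) enlarges the parent study's sample "in order to account for an anticipated 20 percent loss to follow-up over a one-year period". The Objective 3 hypothesis in Section 2.2 is that post-renovation chemical exposures differ from pre-renovation ones and that "differences between renovated and non-renovated homes will be observed"; it gives no direction.

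**The concern.** The example describes 35 independent units per group, while the rest of the protocol describes 32 homes. The text says participants, and an index child plus a sibling could bring the number of children above 35. That does not help, because the outcome is a home-level air concentration and a second child adds no second air sample.

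The figure also depends on two choices a reader cannot see, and on every home being retained. It is the only pilot-specific statement of detectable difference, since the other calculations belong to the 13-site parent study. Anyone judging what the renovated versus non-renovated contrasts can show will start from 11.9.

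**Working it through.** **Formula.** Appendix A, Equation 1, is m = D · 2(z_α + z_power)² · {1 + (n − 1)ρ} / (nΔ²), with Δ = d/SD. Solved for the difference:

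d = SD · √[ 2D (z_α + z_power)² {1 + (n − 1)ρ} / (n m) ]

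**Inputs.** From Section 2.3: SD = 19.4, D = 2.0, ρ = 0.3, power 0.80 (z = 0.842), alpha 0.05. From Appendix A, Equation 1: n = 3 repeated measures. With n = 3, {1 + 2(0.3)}/3 = 0.5333.

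**Reproducing 11.9 at m = 35.**
- One-sided (z = 1.645): (1.645 + 0.842)² = 6.183. Then 2 × 2.0 × 6.183 × 0.5333 / 35 = 0.3768, with square root 0.614. 0.614 × 19.4 = **11.91**, which matches.
- Two-sided (z = 1.960): (1.960 + 0.842)² = 7.849. The same steps give 0.692 × 19.4 = 13.42, which does not match.
- Other numbers of measures, one-sided: n = 1 gives 16.31, n = 2 gives 13.15, n = 4 gives 11.24.
- Other numbers of measures, two-sided: n = 1 gives 18.37, n = 2 gives 14.81, n = 4 gives 12.66. Two-sided n = 6 gives 11.86, but the pilot has only four visits (Section 4.1).

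So, up to the four visits available, only three measures with a one-sided test give 11.9.

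**Cross-check on sidedness.** The parent tables show the same habit. For effect size 0.30 and correlation 0.5, Equation 1 gives 13.26 buildings one-sided and 16.84 two-sided; Table 21 states 13. For the first two formaldehyde rows of Table 22 it gives 408.8 and 75.1 one-sided, against 518.9 and 95.3 two-sided; the table states 408 and 75.

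**Corrected inputs (n = 3, D = 2.0).** A 20% loss from 32 leaves 25.6, taken as 26.

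| Homes per group | One-sided: difference (power for 11.9) | Two-sided: difference (power for 11.9) |
|---|---|---|
| 35 | 11.91 (80%) | 13.42 (70%) |
| 32 | 12.45 (77%) | 14.03 (66%) |
| 26 | 13.82 (69%) | 15.57 (57%) |

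For example, at 32 homes two-sided: 2 × 2.0 × 7.849 × 0.5333 / 32 = 0.5233, with square root 0.723, and × 19.4 = 14.03. Rounding the loss to 25 homes instead gives 14.09 one-sided and 15.88 two-sided. A two-sided test with 80% power for 11.9 needs 45 analysed homes per group.

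**Log scale (assuming log-normality).** The log-SD is √ln(1 + (19.4/15.0)²) = √ln 2.673 = 0.99. Two-sided, 0.723 × 0.99 = 0.717 at 32 homes and 0.803 × 0.99 = 0.796 at 26. These correspond to geometric means lower by 1 − e^(−0.717) = 51% and 1 − e^(−0.796) = 55%.

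**The case against.** The strongest reply is that the documented slip is small. Moving from 35 to 32 on the document's own method changes 11.9 to 12.45 and costs about 3 power points. That stands: most of the wider gap comes from sidedness and loss.

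Sidedness and the number of measures are inferred from the reproduction. The parent VOC hypotheses are directional (lower in green homes), and Section 2.2 says the add-on supports them, so a one-sided test could be defended. This also stands, which is why both sets of figures are given. What cannot be defended is leaving the choice unstated beside a non-directional pilot hypothesis.

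With all four visits as repeated measures, one-sided and no loss, 32 homes give 11.75 (81% power). But this counts the pre-renovation visit as outcome, is not the calculation that yields 11.9, and gives 13.04 at 26 homes.

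The 20% is a one-year allowance from the parent study. Baseline part 2 comes one week after renovation, so later dropouts still contribute some data. Applying 26 to every measure is therefore the pessimistic end of the range.

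Three stronger readings are tempting, and the documents do not support them:
- A reader might infer that 35 homes per group is impossible. Section 3.2 calls 32 and 32 a target; the stated maximum of 64 is for siblings. The figure is inconsistent with the design, not ruled out by it.
- A reader might put the design effect of 3.6 from Table 22 in place of 2.0. Multiplying by √(3.6/2.0) = 1.342 turns 14.03 and 15.57 into 18.8 and 20.9. But that value comes from cockroach-allergen clustering in another study's buildings, and Appendix A uses 1.2 for asthma outcomes. Nothing establishes 3.6 for limonene.
- A reader might infer that the section presents a null result as informative. It does not. It offers one example, Section 2.4 calls sample size the biggest limitation, and Section 5 warns of limited power for the exploratory asthma analysis.

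**Conclusion.** The 11.9 µg/m³ figure does not belong to this design and should be restated. On the document's own one-sided calculation with three measures, the detectable difference is 12.5 µg/m³ at 32 homes per group and 13.8 at 26. With a two-sided 5% test, which fits Objective 3 as worded, it is 14.0 and 15.6. At the last figure even complete removal of limonene from an assumed mean of 15.0 would fall short of 80% power on the arithmetic scale. That comparison is specific to the arithmetic scale: on the log scale the same inputs correspond to a 51–55% lower geometric mean.

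These results rest on the stated SD, design effect and correlation, on three measures per home, and on the parent plan's 20% loss carried over to the pilot. The correction is worth making but not critical, since no enrolment decision or stopping rule depends on this example and the protocol already admits a limited sample.

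**What to change.** Rewrite the example in Section 2.3:
- Replace 35 participants with 32 enrolled and about 26 retained homes per group, and name the home as the unit.
- State the sidedness of the 5% test and the number of repeated measures.
- Give the detectable difference as 14.0–15.6 µg/m³ two-sided, or 12.5–13.8 if one-sided testing is kept and declared.
- Optionally add the log-scale equivalent, about a 51–55% lower geometric mean for the two-sided case, with the log-normal assumption stated. Table 8 plans geometric means, so this is closer to the intended summary.
- If values at a design effect of 3.6 are shown, label them as a sensitivity analysis.

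The cost is one paragraph and a less favourable figure. Recruitment, visits and sampling do not change.

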2.4 Strengths and Limitations

There are several strengths to this EPA pilot study add-on, including, a large cohort of children; siblings; longitudinal design; opportunity to collect multimedia measurement information for consumer product active ingredients. Additionally, by collaborating on this study, EPA can wisely use its limited resources to collect non-chemical stressor information.

We recognize and acknowledge that there are also limitations to this EPA pilot study add-on. The biggest limitation is the sample size, which is fixed and dependent on CDC's grantee's ability to recruit and retain participants throughout the time period of the study. In the main Green Housing Study, $n=64$ children (ages 7-12 years) with asthma will be enrolled. Therefore, $n=64$ younger siblings (only one sibling per household) will be the maximum number that could be enrolled as part of the EPA pilot study add-on. The sample size of the younger siblings enrolled as part of the EPA pilot study add-on will influence the amount of data available for statistical analyses and thus influence the types of statistical analyses that may be conducted on the data.

2.5 Collaborations and Partnerships

CDC and HUD have a collaboration in place on the Green Housing Study. CDC and EPA have established an interagency agreement to complete the EPA pilot study add-on as part of the Green Housing Study third study site.

In partnership with HUD and CDC, EPA will leverage this opportunity to collect additional multimedia measurements and questionnaire data from the index children actively participating in the Green Housing Study and a sibling from each household in order to characterize personal, housing, and community factors influencing children's potential exposures to indoor contaminants at various lifestages.

The objectives of this EPA pilot study add-on support the research needs of the SHC and CSS national research programs, as well as the specific aims and hypotheses of the Green Housing Study. We believe additional opportunities for data analysis and collaboration will be identified.

Appendix C (The IRB-approved Protocol)

Additional collaborations will be formed as they are identified to complete laboratory analyses or share data for future research efforts. A potential collaboration currently being considered is with Silent Spring Institute to share protocols and methods for collection and analysis of SVOCs in air. Another potential collaboration is with our colleagues in the Office of Research and Development, U.S. EPA who are interested in using the dust samples to enhance the EPA pilot study add-on objectives.

3.0 RESEARCH PROTOCOL

3.1 Overview

This EPA pilot study is an add-on to the third study site of the Green Housing Study and is designed to characterize and assess factors associated with children's exposures to chemical and biological agents to inform asthma morbidity. It will use the information already being collected in the Green Housing Study. In addition, it will collect additional environmental, personal, and biological samples and compile additional information on children's activities, residence, and community. The proposed data collection will improve the understanding of chemical exposure sources, routes, and pathways; further evaluate factors affecting children's contact with chemical residues found in their residential environments; identify non-chemical stressors to be considered for understanding young children's exposures to chemicals; and assess and improve predictive modeling approaches for young children's exposures to chemicals.

